**Figure 2. Interim Analysis Guidelines**

## 5.0 Analysis Populations and Baseline Characteristics

### 5.1 Analysis Populations

The full analysis set (FAS) includes all subjects who received at least 1 dose of study drug. The FAS will be used for all safety, efficacy, and baseline analyses.

**Table 4. Baseline Characteristics**

Variable	Levels
Age	< 65, ≥ 65
Sex	male, female
Race	white, black, Asian, other
Ethnicity	Hispanic, non-Hispanic
Type of myeloma	IgG, IgA, IgD, light chain
Prior lines of therapy	1 – 3, 3 – 6, > 6
Prior therapy with:	
 
• PI + IMiD
 
• PI (bortezomib, carfilzomib, ixazomib)
 
• IMiD (thalidomide, lenalidomide, pomalidomide),
 
• monoclonal antibody (daratumumab, elotuzumab) 
 
• stem cell transplant
 
 
 

BCL-2	low, high
ISS stage	I, II, III
ECOG	0, 1, 2, > 2
t(11;14)	positive, negative
t(4;14)	positive, negative
17p deletion	yes, no
13q deletion	yes, no
Hyperdiploid	yes, no

## 6.0 Efficacy Analyses

### 6.1 Primary Efficacy Analysis

For ORR, exact (binomial) one-sided tests of H0: ORR ≤ 35% vs H1: ORR > 35% at significance levels of 0.025 and 0.1 will be performed for Arms A and B, respectively.

Point estimates and exact (Clopper-Pearson) 95% confidence intervals of ORR for each of the two arms will be calculated.

## **6.2 Efficacy Analysis**

PFS, DOR, and TTP will be analyzed with Kaplan-Meier methodology. Median PFS, DOR, and TTP will be estimated, along with corresponding 95% CIs.

## **7.0 Safety Analyses**

### **7.1 Analysis of Adverse Events**

AE analysis will only include treatment-emergent events (those that have an onset on or after the day of the first dose of any study drug), and will not include AEs that have an onset of more than 30 days after the last dose of any study drug.

Treatment-emergent AEs will be coded and summarized by system organ class and preferred term according to the Medical Dictionary for Regulatory Activities (MedDRA) AE coding dictionary. The percentage of subjects experiencing an AE at a given severity will be provided along with the NCI CTCAE version 4.03 toxicity grade and relationship to the study drugs. Serious AEs, AEs leading to discontinuation of treatment, and AEs leading to death will be summarized. All summaries will be done by dose. For the study as a whole, AEs will be evaluated and summarized.

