	
the cumulative number of subjects who experience a DLT at the current combination dose.
 
The dose-expansion phase of the study will consist of 2 arms. Arm A will further evaluate the safety and efficacy profile of the combination therapy with venetoclax, pomalidomide, and dexamethasone in approximately 23 subjects positive for t(11;14) translocation. Arm B further evaluate the safety and efficacy profile of the combination therapy with venetoclax, pomalidomide, and dexamethasone in approximately 27 subjects negative for t(11;14) translocation. Subjects will receive venetoclax (800 mg PO, QD) + pomalidomide (4 mg PO, QD) + dexamethasone (40 mg qw). All subjects who participate in the dose-expansion phase of the study are required to undergo bone marrow aspirate collection at screening for determination of t(11;14) status before enrollment.

Key Eligibility Criteria:
	
Male or female subjects, at least 18 years old, with a diagnosis of R/R MM. Subjects should meet the following disease activity criteria:
 
 • R/R MM with documented evidence of progression during or after the subject's last treatment regimen based on the investigator's determination of the International Myeloma Working Group (IMWG) criteria. • Measurable disease, defined by at least 1 of the following disease activity criteria: 
 • serum M-protein ≥ 1.0 g/dL (≥ 10 g/L) for immunoglobulin (Ig)G MM • serum M-protein ≥ 0.5 g/dL (≥ 5 g/L) for IgA, IgD, IgE, and IgM MM • urine M-protein ≥ 200 mg/24 hours • serum free-light chain (FLC) ≥ 10 mg/dL provided serum FLC ratio is abnormal • Has received at least 1 prior line of therapy • Must meet all of the following prior antimyeloma treatment parameters: 
 • subject must have received at least 2 consecutive cycles of lenalidomide or a lenalidomide-containing regimen • subject must be refractory to lenalidomide 
 • subject must have documented evidence of progressive disease based on the investigator's determination of response as defined by the modified IMWG criteria on or after the last regimen • subject who received only 1 line of prior treatment must have demonstrated progressive disease on or within 60 days of completion of the lenalidomide-containing regimen

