Subjects must complete at least 80% of pomalidomide dosing and at least 80% of venetoclax dosing in Cycle 1 or experience a DLT to be considered evaluable for dose-escalation decisions. Subjects not DLT-evaluable may be replaced as necessary to meet minimum requirement for dose escalation. DLTs are defined in Section 6.5.

Additional information regarding the BOIN design will be provided in the SAP.

During Part 1, dose review meetings will be conducted at the completion of Cycle 1 in at least 3 evaluable subjects in each cohort.

All subjects who participate in the dose-escalation phase of the study will undergo bone marrow aspirate collection for cytogenetic determination at baseline.

Part 2: Dose Expansion

[figure not shown]
The dose-expansion phase of the study will consist of 2 arms. Arm A will further evaluate the safety and efficacy profile of the combination therapy with venetoclax, pomalidomide, and dexamethasone in approximately 23 subjects positive for t(11;14) translocation. Arm B will further evaluate the safety and

efficacy profile of the combination therapy with venetoclax, pomalidomide, and dexamethasone in approximately 27 subjects negative for t(11;14) translocation. Subjects will receive the venetoclax dose that is determined to be safe in Part 1 + pomalidomide (4 mg PO, QD) + dexamethasone (40 mg qw). All subjects who participate in the dose-expansion phase of the study are required to undergo bone marrow aspirate collection at screening for determination of t(11;14) status before enrollment.

See Section 5.1 for information regarding eligibility criteria.

Review of the efficacy and safety data will be completed on an ongoing basis. During Part 1, dose review meetings will be conducted at the completion of Cycle 1 with at least 3 evaluable subjects in each cohort. Additional reviews will be held as deemed necessary based on study events or data.

Figure 1. Study Design

Dex = dexamethasone; Pom = pomalidomide; QD = once daily; qw = once weekly; Ven = venetoclax

Note: Venetoclax will be administered once daily from Day 1 through Day 28 of each cycle. Pomalidomide will be administered once daily from Day 1 through Day 21 of each cycle.

Hematology must be completed before the initiation of each subsequent cycle of combination therapy. Subjects must meet the following minimum criteria to continue combination therapy:

- absolute neutrophil count (ANC) $\geq 500/\mu\text{L}$; growth factor support is allowed after Cycle 1

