MM subjects with high tumor burden (e.g., high bone marrow plasma cell infiltration, plasma cell leukemia, or bulky plasmacytomas), rapidly increasing M-protein or light chains or high proliferative activity, plasmablastic morphology, or compromised renal function (CrCL < 50 mL/minute) may be at higher risk of developing TLS.¹¹ Additionally, subjects with t(11;14) and high bone marrow plasma cell infiltration or a significant number of circulating plasma cells appear to have an increased risk for TLS when treated with venetoclax.

Consider TLS prophylaxis with oral hydration (at least 1 to 2 L, as tolerable) in all subjects at least 72 hours before the first day of dosing with venetoclax and pomalidomide. Prophylaxis with uric acid reducing agents may be required for subjects with high uric acid levels. Monitor for clinical and laboratory evidence of TLS during treatment ([Appendix G](#)) and manage abnormalities in serum creatinine, uric acid, and electrolytes promptly according to institutional guidelines (guidance also available in [Appendix H](#)).

For subjects with t(11;14) and > 50% bone marrow plasma cell infiltration or CrCL < 50 mL/minute, oral hydration as aforementioned is required and chemistry laboratory tests (phosphate, potassium, calcium, uric acid, creatinine, lactate dehydrogenase, and AST at a minimum) should be done at approximately 6 hours after the first dose with venetoclax. Consider uric acid-lowering drugs in subjects at higher risk for TLS. More intensive measures (e.g., IV hydration, frequent monitoring of laboratory values, hospitalization, etc.) should be considered at the investigator's discretion or in accordance with institutional guidelines. All TLS prophylaxis measures should be appropriately recorded in the eCRF.

In case of evidence of TLS, dosing with venetoclax should be interrupted. Drug interruption for up to 72 hours following transient (i.e., lasting < 48 hours) chemical changes and laboratory TLS will not require a dose reduction. If the TLS has not resolved within 72 hours, then a dose reduction should be considered. The subject may be allowed to re-escalate to the final dose based on a risk assessment (including tumor burden status). If active correction of electrolytes was performed, the first dose of

venetoclax should only be given when electrolytes have been stable without additional treatment for at least 24 hours.

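### AE summaries are planned only by dose and for the whole study, which merges t(11;14)-positive Arm A with t(11;14)-negative Arm B although each arm is meant to evaluate safety

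*SAP*

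**What the plan says.** SAP 7.1 (Analysis of Adverse Events) sets two groupings for AEs. The first is "All summaries will be done by dose". The second is "For the study as a whole, AEs will be evaluated and summarized". SAP 7.2 (laboratory data) and 7.3 (vital signs) add no grouping by arm or by t(11;14) status, and SAP 5.1 uses the undivided full analysis set for safety. Protocol 6.2 and 7.5 leave safety analysis to the SAP, so no other text supplies an arm-level table.

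Protocol 4.1 gives both arms a safety aim. For Arm A: "Arm A will further evaluate the safety and efficacy profile of the combination therapy with venetoclax, pomalidomide, and dexamethasone in approximately 23 subjects positive" for the translocation. Arm B has the same aim, covering the safety and "efficacy profile of the combination therapy with venetoclax, pomalidomide, and dexamethasone in approximately 27 subjects negative for t(11;14) translocation".

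Both arms are treated alike. Protocol 4.1 says: "Subjects will receive the venetoclax dose that is determined to be safe in Part 1". The synopsis instead names 800 mg once daily. Either way, one venetoclax dose applies to both arms, with the same pomalidomide and dexamethasone.

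Efficacy is handled differently. Protocol 7.4 and SAP 6.1 test ORR and give exact intervals separately for Arms A and B.

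On TLS, Protocol 6.4 says that subjects who have t(11;14) together with either high marrow plasma cell infiltration or a significant number of circulating plasma cells "appear to have an increased risk for TLS when treated with venetoclax". TLS is the only AE of special interest listed in Protocol 6.1. SAP section 7 names no TLS summary.

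**The concern.** Dose cannot separate the two arms, because dose is what they share. If SAP 7.1 is followed as written, the planned tables contain no AE rate for Arm A or for Arm B, even though evaluating safety is part of each arm's stated purpose and characterizing safety is the study's primary objective (Protocol 3.1). A reader of the results would have ORR for each t(11;14) population but only a merged safety profile to set beside it.

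If a toxicity differed between the two populations, the merged column would show a weighted average: too low for the arm at higher risk and too high for the other. The protocol itself gives one reason to look, since it uses t(11;14) status with marrow infiltration when it identifies TLS risk and when it sets the 6-hour chemistry check. The planned AE analysis does not use t(11;14) status at all.

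**Working it through.** The plan states no figure on this point, so there is none to reproduce. The check has two steps.

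**Step 1. Which rows of data fall in which column?**

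| Group | t(11;14) | Approximate size | Venetoclax dose | Column under SAP 7.1 |
|---|---|---|---|---|
| Part 2 Arm A | positive | 23 | Part 2 dose | Part 2 dose |
| Part 2 Arm B | negative | 27 | Part 2 dose | Part 2 dose |
| Part 1 cohort at that dose | either (Protocol 5.1, criterion 10) | 3 to 6 (Protocol 7.2) | same | Part 2 dose |

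The by-dose column holds 23 + 27 = 50 Part 2 subjects, or 53 to 56 with the Part 1 cohort. The whole-study column pools further. Neither isolates an arm.

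**Step 2. What does pooling do to a rate?**

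For true or observed rates rA and rB, the pooled Part 2 rate is

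(23·rA + 27·rB)/50 = 0.46·rA + 0.54·rB.

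If rA = rB, pooling loses nothing. If every event is in Arm A (rB = 0), the pooled rate is 23/50 = 46% of the Arm A rate.

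The documents give no TLS rate, so the counts below are assumptions. Intervals are Clopper-Pearson 95%: the lower limit is the 0.025 quantile of Beta(x, n−x+1) and the upper limit the 0.975 quantile of Beta(x+1, n−x). For zero events the upper limit is 1 − 0.025^(1/n); with n = 27 this is 12.8%.

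| Events A, B | Arm A (n = 23) | Arm B (n = 27) | Pooled Part 2 (n = 50) |
|---|---|---|---|
| 2, 0 | 8.7% (1.1 to 28.0) | 0% (0 to 12.8) | 4.0% (0.5 to 13.7) |
| 3, 0 | 13.0% (2.8 to 33.6) | 0% (0 to 12.8) | 6.0% (1.3 to 16.5) |
| 4, 0 | 17.4% (5.0 to 38.8) | 0% (0 to 12.8) | 8.0% (2.2 to 19.2) |
| 5, 1 | 21.7% (7.5 to 43.7) | 3.7% (0.1 to 19.0) | 12.0% (4.5 to 24.3) |

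If Part 1 contributes 3 to 6 event-free subjects to the column, 3 events become 3/53 = 5.7% to 3/56 = 5.4%.

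The first three rows are the extreme case. In the last row the pooled rate is 12.0/21.7 = 55% of the Arm A rate. The intervals for the two arms overlap in every row. For 3 against 0, Fisher's exact two-sided p is C(23,3)/C(50,3) = 1771/19600 = 0.09: the opposite extreme, with all 3 events in Arm B, has probability 2925/19600, which is larger and so is not added.

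**The case against.** By dose is a defensible main display. The primary objective covers relapsed or refractory myeloma as a whole, the regimen is identical in the two arms, and no safety comparison between arms is planned. That stands, and it is why the pooled table should stay. It does not supply the arm-level evaluation that Protocol 4.1 assigns to each arm.

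Four stronger readings are tempting, and the documents do not support them.

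- *That arm-specific AE rates cannot be produced.* SAP 7.1 fixes a grouping but does not forbid others, and t(11;14) status is a baseline variable in SAP Table 4. The supportable statement is that arm-level summaries are not pre-specified. Tables added after open-label data have been seen carry less weight than planned ones.
- *That the final go/no-go decision is made per arm and so lacks its safety input.* SAP 4.5 breaks the interim ORR guidelines down by arm. Its statement on the final decision refers to the whole of the efficacy and safety data and does not say per arm. The same section provides for continuous monitoring of both arms.
- *That the protocol expects more TLS in t(11;14)-positive disease as such.* Protocol 6.4 requires t(11;14) together with high infiltration or many circulating plasma cells, hedges the statement, and also lists risk factors unrelated to t(11;14), such as renal function. An arm split therefore would not isolate the subjects at risk; it would only place the t(11;14)-related ones in the right denominator.
- *That a TLS signal would go unseen.* TLS must be entered within 24 hours of site awareness, and SAP 7.2 plans subject listings of Grade 3 to 4 chemistry values. A few cases would be noticed individually. What is missing is a planned rate by population, for TLS and for AEs in general.

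It is also fair to say that arm-level rates from 23 and 27 subjects are imprecise. That argues for keeping them descriptive. The same numbers are accepted for formal ORR tests by arm.

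**Conclusion.** The point holds as a gap in what is pre-specified. SAP 7.1 plans AE summaries by dose and for the whole study only, and because the Part 2 arms share one dose, those tables merge two populations that the design separates and that ORR reports separately.

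The possible distortion is bounded. It is nil if the arms have equal rates, and at most a reduction to 46% of the Arm A rate if all events fall there, or slightly lower with Part 1 subjects in the column. The example of 13.0% in Arm A shown as 6.0% pooled rests on assumed counts at that extreme and is not a forecast. The conclusion itself needs no assumed rate: it rests on the stated grouping, the common Part 2 dose and the safety aim given to each arm. The gap is descriptive and recoverable from data already collected, so this is a low-cost improvement that should be made; it does not threaten the validity of the study.

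**What to change.** Amend SAP 7.1 so that AE summaries are presented descriptively in four groupings: by Part 1 dose cohort, by Part 2 arm (A and B), pooled by dose, and overall. Apply them to treatment-emergent AEs, Grade 3 or higher events, serious AEs, AEs leading to discontinuation or death, TLS and infections. Several of these summaries are already planned and only need the extra columns; TLS and infections would be named as additional rows or tables. Use the same grouping for the laboratory grade summaries in SAP 7.2. State that no formal comparison between arms is intended and that arm-level rates will be imprecise.

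The cost is additional table columns and a short SAP amendment. Arm is fixed at enrollment and already in the data, so no change to study conduct, sample size or data collection is needed.

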### **7.2 Analysis of Laboratory Data**

Where applicable, laboratory values will be categorized according to the NCI CTCAE version 4.03 grades. Changes from baseline to maximum grades, as well as final post-baseline grades will be assessed. The baseline and final grades will be defined as: the grade of the last measurement collected prior to the first dose of any study drug, and the grade of the last post-baseline measurement collected no more than 30 days after the last dose of any study drug, respectively. If multiple values are available for a post-baseline measurement, then the value with the highest NCI CTCAE grade will be used.

Detailed listings of data for subjects experiencing NCI CTCAE Grade 3 – 4 blood chemistry and hematology values will be provided. All collected measurements may be included in these listings, regardless of the number of days after the last dose of any study drug.

### **7.3 Analysis of Vital Signs and Weight**

Detailed listings of data for subjects experiencing potentially clinically significant vital sign values (according to the AbbVie-defined criteria) will be provided. All collected measurements may be included in these listings, regardless of the number of days after the last dose of any study drug.

## Appendix A. Bayesian Optimal Interval Design

### A.1 Methodology

Let  $\phi$  denote the pre-specified target toxicity rate. Let  $\Delta_L > 0$  and  $\Delta_U > 0$  be pre-specified lower and upper cutoffs, respectively, which satisfy  $0 < \phi - \Delta_L < \phi + \Delta_U < 1$ . The BOIN design consists of determining  $\Delta_L$  and  $\Delta_U$  such that the interval  $(\phi - \Delta_L, \phi + \Delta_U)$  minimizes the probability of incorrect dose assignment decisions. To determine  $\Delta_L$  and  $\Delta_U$ , consider three hypotheses at dose level  $j$ :

$$H_{0j}: p_j = \phi, \quad H_{1j}: p_j = \phi_l, \quad H_{2j}: p_j = \phi_2$$

where  $p_j$  denotes the true toxicity rate at dose level  $j$ ,  $\phi_l$  denotes the highest toxicity rate that is deemed subtherapeutic such that dose escalation should be made and  $\phi_2$  denotes the lowest toxicity rate that is deemed overly toxic such that dose de-escalation should be made. Thus, the correct dose assignment decisions under  $H_{0j}$ ,  $H_{1j}$  and  $H_{2j}$  are retainment (i.e., stay at current dose), escalation and de-escalation, respectively.

Assuming an equal prior probability of the three hypotheses being true (i.e.,  $\Pr(H_{0j}) = \Pr(H_{1j}) = \Pr(H_{2j}) = 1/3$ ), the optimal interval  $(\phi - \Delta_L, \phi + \Delta_U)$  which minimizes the probability of incorrect dose assignment decisions is given by:

$$\phi - \Delta_L = \frac{\log\left(\frac{1-\phi_1}{1-\phi}\right)}{\log\left(\frac{\phi(1-\phi_1)}{\phi_1(1-\phi)}\right)} \quad \text{and} \quad \phi + \Delta_U = \frac{\log\left(\frac{1-\phi}{1-\phi_2}\right)}{\log\left(\frac{\phi_2(1-\phi)}{\phi(1-\phi_2)}\right)}$$

Suppose the current dose is  $j$  where  $j = 1, \dots, J$ . Let  $\hat{p}_j = (y_j/n_j)$  denote the estimated toxicity rate based on the accumulated information on dose combination  $j$  with  $y_j$  toxicities and  $n_j$  subjects. Define an admissible dose escalation set as  $A_E = \{(j+1)\}$  and an admissible dose de-escalation set as  $A_D = \{(j-1)\}$ . Dose assignment decisions under the BOIN design proceeds as follows:

1. Treat the first cohort at the starting dose combination.

2. Suppose the current cohort is treated at dose combination  $j$ ; then for the next cohort of patients:
  - a. If  $\hat{p}_j \leq \phi - \Delta_L$ , escalate to the next higher dose combination that belongs to  $A_E$ . If  $j = J$ , the current dose combination is retained.
  - b. If  $\hat{p}_j \geq \phi + \Delta_U$ , de-escalate to the next lower dose combination that belongs to  $A_D$ . If  $j = 1$ , the current dose combination is retained.
  - c. Otherwise, if  $\phi - \Delta_L < \hat{p}_j < \phi + \Delta_U$ , the current dose combination is retained.
3. This process continues until the total sample size is exhausted or the study is terminated early due to excess toxicity (as described below).

The BOIN design also imposes the following safety rule: dose combinations which satisfy  $Pr\{p_j > \phi | y_j\} \geq \lambda$  are eliminated, where  $\lambda$  is a pre-specified threshold probability.

## A.2 Application to Study M16-085

If possible, only the venetoclax dose will be increased. The pomalidomide and dexamethasone doses will be fixed in both available cohorts during the dose escalation part of the study.

For Study M16-085, the toxicity rates and safety threshold are pre-specified as follows:

$\phi = 0.30$  (target toxicity rate)

$\phi_1 = 0.6\phi$  (highest toxicity rate which is subtherapeutic)

$\phi_2 = 1.4\phi$  (lowest toxicity rate which is overly toxic)

$\lambda = 0.95$  (safety threshold for dose combination elimination)

The above pre-specified values yield an optimal interval of (0.236, 0.359). Approximately 6 – 12 subjects may be enrolled in cohorts of at least 3. The

corresponding BOIN design decision rules (based on the cumulative number of patients who experience a DLT at the current dose combination) are presented in [Table 5](#).

**Table 5. Dose-Escalation Decision Rules**

Action	Number of DLT-Evaluable Subjects Treated at Current Combination							
	3	4	5	6	7	8	9	10
Escalate if number of subjects with DLT $\leq$	0	0	1	1	1	1	2	2
Stay at current combination if number of subjects with DLT =	1	1	-	2	2	2	3	3
De-escalate if number of subjects with DLT $\geq$	2	2	2	3	3	3	4	4
Eliminate a if number of subjects with DLT $\geq$	3	3	4	4	5	5	5	6

DLT = dose-limiting toxicity

a. Eliminate current and higher combinations (i.e., venetoclax dose and pomalidomide dose  $\geq$  current dose level).
